6.3 Quality of life endpoints

- Change from baseline by visit up to EOT in SF-36v2™ Health Survey domain and component scores.

6.4 Pharmacoeconomic endpoints

- Change from baseline by visit up to EOT in WPAI:MS scores.
- Health care resource utilization from baseline by visit up to EOT on-treatment visit (number of hospitalizations, length of stay, number of intensive care admissions for MS relapse and visits to an emergency medical services facility for MS).

6.5 Pharmacokinetic and pharmacodynamic endpoints

6.5.1 Pharmacokinetic evaluations

- Plasma concentrations of ponesimod pre-dose at Week 12, Week 24, Week 48, Week 96, Week 144, EOT and FU, and 3 hours post-dose on Day 1 and at Week 12.

6.5.2 Pharmacodynamic evaluations

- Absolute and percent change in peripheral blood lymphocyte counts pre-dose by visit up to EOS.
- Absolute and percent changes in lymphocytes subsets by visit up to EOS [sub-study; see Section [3.6.1](#)].

6.5.3 PK/PD relationship

- Correlation of selected efficacy and safety variables with absolute lymphocyte counts and magnitude of reduction of lymphocyte counts may be analyzed.

7 STUDY ASSESSMENTS

All study assessments are performed by a qualified study staff member: medical, nursing, or specialist technical staff, and are recorded in the eCRF, unless otherwise specified. Study assessments performed during unscheduled visits will also be recorded in the eCRF.

If the principal investigator delegates any study procedure/assessment for a subject, e.g., ECG, MRI, blood sampling etc., to an external facility, she/he should inform Actelion to whom these tasks are delegated. The set-up and oversight will be agreed upon with Actelion. The supervision of any external facilities remains under the responsibility of the principal investigator.

Calibration certificates for the following devices used to perform study assessments must be available prior to the randomization of the first subject:

- Temperature measurement devices for study medication storage area and lab sample storage (e.g., freezer).
- Spirometer; in addition, a copy of the calibrations check (syringe check) of the day of measurement must be stored and a log of calibration check results must be maintained at the site [see Section 7.3.3].
- ECG recorder.
- BP monitoring device.
- MRI; in addition, prior to the start of the study, each MRI site must be qualified by the MIAC [see Section 7.2.3].

7.1 Screening/baseline assessments

7.1.1 Informed consent (Visit 1 [Screening])

Prior to performing any study-specific procedures or assessments, the subject must provide written informed consent to participate in the study. If the signing of informed consent and performance of the first study-specific procedures or assessments take place on the same day, it must be clear from the source documents that informed consent was obtained prior to any study-specific procedures being performed. If a study-specific procedure or assessment has been performed as part of routine assessments and the results are available prior to the subject's signing of informed consent, such procedure or assessment may be used to assess eligibility and does not have to be repeated (e.g., CXR [see Section 7.3.4]). In such cases, it must be clear from the source document when and for which reason the assessment was done prior to the signing of the informed consent. It

is the responsibility of the principal investigator / treating neurologist to explain the study in all its aspects to the subject and obtain her/his informed consent. The informed consent process will be documented in the investigator site file. The oral and written information about the trial, as well as the ICF, will be provided in a language that is fully understandable to the subject.

For subjects who provide informed consent but are subsequently not randomized into the study, the reasons for not being randomized will be recorded in eCRF.

In order to ensure subjects are made aware of potential risks and benefits of continuing in the study as well as alternative treatment options available, subjects who continue study treatment and DMF background therapy upon experiencing a confirmed relapse or a 24-week CDA while on study drug will be asked to re-consent to continue receiving study treatment.

7.1.2 Baseline demographics and disease characteristics

Baseline demographics (sex, age, race, ethnicity, body weight, height, and childbearing potential [if applicable]) are to be recorded in the eCRF at Visit 1 (Screening). Complete, clinically relevant medical history and current conditions, as well as smoking status and MS disease characteristics [see Section 4.6] are to be documented in the eCRF.

7.1.3 Study-concomitant therapies

All study-concomitant therapy (including contraceptives and traditional and alternative medicines, i.e., plant-, animal-, or mineral-based medicines) taken by the subject from the signing of informed consent until the end of their participation in the study (i.e., EOS) will be recorded in their respective forms (i.e., Concomitant Medications form or Contraceptive Methods form) of the eCRF. This includes all ongoing therapies and those initiated or stopped during this period. The corresponding dates of initiation and discontinuation will be recorded [see Section 5.2.2.1].

7.1.4 Previous MS therapies

Any previous administration of disease-modifying treatment for MS (e.g., IFN β -1a [Rebif[®] - Avonex[®], Plegridy[®]], IFN β -1b [Betaseron[®], Betaferon[®], Extavia[®]], glatiramer acetate [Copaxone[®], Glatopa[®]], natalizumab [Tysabri[®]], teriflunomide [Aubagio[®]], fingolimod [Gilenya[®]], mitoxantrone [Novantrone[®]], alemtuzumab [Lemtrada[®]], daclizumab [Zynbryta[®]], ocrelizumab [Ocrevus[®]], cladribine [Mavenclad[®]]), at any time prior to Visit 1 (Screening) will be recorded in the previous MS treatment form of the eCRF [see Sections 1.1.4 and 5.2.2.2].

7.2 Efficacy assessments

7.2.1 Neurological evaluation

EDSS and FS scores [Kurtzke 1983] are based on a standard neurological examination for assessing neurologic disability and impairment in MS. The seven FS scores are ordinal clinical rating scales ranging from 0 to 5 or 6, assessing visual, brain stem, pyramidal, cerebellar, sensory, bowel and bladder, and cerebral functions while ambulation is an ordinal scale ranging from 0 to 12 assessing walking distance and assistance. The ratings of the individual FS scores are then used, in conjunction with ambulation score, to obtain the EDSS score. EDSS is an ordinal clinical rating scale ranging from 0 (normal neurological examination) to 10 (death due to MS) in half-point increments.

EDSS and FS assessments will be performed at Visit 1 (Screening), Visit 2 (Baseline), Visit 6 (Week 12) and every 12 weeks thereafter until Visit 18 (EOT), Visit 20 (FU), and at any unscheduled visit in the event of relapses (R1, R2, etc.) or other unscheduled visits (U1, U2, etc.). If applicable, EDSS and FS will also be assessed at the corresponding visits in the PTOP (Visits 6A to 18A).

EDSS and FS assessments will only be performed by the efficacy assessor who should preferably maintain this role for a given subject throughout the study [see Section 3.7.3]. The efficacy assessor must not consult prior EDSS/FS scores when performing the current EDSS/FS assessment. In no case will the treating neurologist alter the EDSS/FS score obtained by the efficacy assessor. The examination will be based on the modified neurological examination ‘Neurostatus’ [Appendix 1] using the corresponding scoring documents. The EDSS/FS scoring will be recorded in the eCRF. **NB:** Fatigue, which is an optional part of the ‘Neurostatus’ assessment will not contribute to the Cerebral FS score.

7.2.2 Detection and evaluation of relapses

Detection and evaluation of relapses will be done as follows [see Figure 3]:

Step 1: At every study visit, subjects are reminded to contact their principal investigator / treating neurologist immediately in the event of the appearance of any new or worsening neurological symptoms. In addition, the site will contact the subject in-between the 12-weekly visits (e.g., Visit 6 – Week 12, Visit 7 – Week 24, ...) even after possible premature discontinuation from the study treatment (e.g., Visit 6A – Week 12 in the PTOP, Visit 7A – Week 24 in the PTOP, ...) in order to proactively inquire about any new or worsened neurological symptoms. These telephone calls will be conducted either at Weeks 18, 30, 42, 54, 66, 78, 90, 102, 114, 126, 138 and 150 (\pm 7 days), or 6 weeks after the last 12-weekly visit (\pm 7 days).

Whenever between visits a subject experiences any new or worsening neurological symptoms he/she must contact the principal investigator / treating neurologist, study nurse or clinical coordinator as soon as possible in order to complete a telephone questionnaire for relapse assessment [see [Appendix 12](#)].

If, during the call from the site inquiring about symptoms suggestive of potential new relapses, the subject reports occurrence of such symptoms, a telephone questionnaire for relapse assessment will also be completed.

If a relapse is suspected, the subject will be required to come to the site for an unscheduled relapse assessment visit. The completed telephone questionnaire will be collected in the eCRF.

Step 2: At every scheduled and unscheduled visit (limited to unscheduled visits when the subject will meet with the principal investigator / treating neurologist, but not at other unscheduled visits conducted for repeat testing (e.g., spirometry, liver enzymes), the principal investigator / treating neurologist will interview and examine the subject to determine whether or not a relapse may have occurred since last visit using a dedicated relapse assessment questionnaire [see [Appendix 12](#)] and the relapse symptom form [see [Appendix 13](#)].

Based on the interview and examination, the principal investigator / treating neurologist will determine if symptoms are likely to be due to a relapse (i.e., all elements from the relapse definition in Section [6.1.1](#) have been verified, in the absence of another, better explanation of the subject's symptoms). If so, the subject will be referred to the efficacy assessor for an EDSS assessment (Note: at scheduled visits the EDSS assessment planned for this visit will be used). The completed questionnaire [see [Appendix 12](#)] and the outcome of the examination [see [Appendix 13](#)] will be collected in the eCRF.

Step 3: The efficacy assessor will perform the EDSS/FS assessment within 7 days after the onset of new or worsening neurological symptom(s) [see Section [7.2.1](#)]. **Important note:** EDSS and FS assessments will be performed only by the efficacy assessor. The efficacy assessor must not consult prior EDSS/FS scores when performing the current EDSS/FS assessment. In no case will the treating neurologist alter the EDSS/FS score obtained by the efficacy assessor. If the relapse requires treatment with corticosteroids [see Section [5.2.4](#)], treatment should be initiated as early as recommended by local clinical practice. The blinded neurological examination by the efficacy assessor must always be performed prior to the treatment start.

Step 4: The treating neurologist will review the EDSS/FS score obtained by the efficacy assessor and determine presence or absence of qualifying increase in EDSS/FS (i.e., of the magnitude described in Section [6.1.1](#) from a previously clinically stable EDSS/FS score and consistent with the subject's new symptoms). Based on this review, the treating

[figure not shown]
neurologist will decide if the relapse is confirmed or not, according to the protocol definition of confirmed relapse [see Section 6.1.1]. After the occurrence of each confirmed relapse, subjects will be asked to re-consent to continue receiving study treatment [see Section 13.3].

Once step 1 of the relapse detection has been initiated (whether by subject calling the site, by interview of the subject at scheduled visit, or by scheduled calls from the site to the subject), the final result of the relapse detection and confirmation process will be captured as one of the following three outcomes: no relapse, unconfirmed relapse, or confirmed relapse. New or worsened neurological symptoms reported by the subject and for which there is another better explanation for the subject's current symptoms than an MS relapse will be captured on an AE page.

All MS relapses, whether or not confirmed, must be reported on specific relapse pages of the eCRF. MS relapses and associated symptoms are not to be entered on the AE page of the eCRF with the following exceptions:

- MS relapses with fatal outcome (these must always be recorded as an AE on the AE page in addition to being reported as SAEs).
- MS relapses that, in the view of the investigator, warrant specific notice due to unusual frequency, severity or remarkable clinical manifestations (these should be reported as an AE on the AE page of the eCRF and, if applicable, on the SAE form).

Figure 3 Flow diagram for the detection and evaluation of relapses

* If time of onset of relapse is within 24 hours before the visit, then defer the neurological examination and EDSS/FS assessment by 24 hours.

** If appropriate (e.g., subject has a fever or an infection which can explain the symptoms, or if there is another and better explanation for the patient's current symptoms than an MS relapse), enter subject's symptoms or diagnosis on the AE page.

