1.3.2.4 Safety and tolerability

Clinical studies to date have identified transient changes in heart rate (HR) and atrioventricular (AV) conduction as the most prominent safety-related signal with ponesimod. Oral doses of ponesimod resulted in dose-dependent sinus rate reductions in all treated subjects; the changes were transient and resolved largely within 6–10 hours after dosing. In some subjects, these HR reductions were accompanied by a transient effect on AV conduction with prolongation of the PR interval on the electrocardiogram (ECG) and, occasionally, second degree AV-block. The effects on HR and AV conduction diminish with repeated administration of ponesimod, indicating desensitization. To minimize the first-dose effects on HR and AV conduction, a dose up-titration regimen was successfully tested and is implemented in current clinical trials.

Breathing difficulties and pulmonary function test (PFT) changes have also been detected in humans. Mild transient dyspnea/cough was noted frequently 2–6 hours after an oral dose of 40 mg or higher, and was associated with a clinically relevant forced expiratory volume in 1 second (FEV₁) decrease from baseline. Symptoms resolved spontaneously upon discontinuation of treatment with ponesimod, and PFTs returned to baseline upon drug discontinuation. In study AC-058B201, dyspnea AEs were reported in 6.1% of patients in the ponesimod 20 mg group as compared to 3.3% in the placebo group. Accordingly 13.5% of patients in the ponesimod 20 mg group had FEV₁ < 80% of their baseline measurements at least once during the treatment period compared to 3.3% in the placebo group. However, none of the patients in the 20 mg group discontinued treatment due to a respiratory AE. Doses higher than 20 mg were associated with decreased tolerability; there were increased discontinuation rates with 40 mg mainly due to more pronounced pulmonary function effects and an increased incidence of liver enzyme elevations.

Data from an interim analysis of the long-term extension study AC-058B201/B202 with a cut-off date of 31 October 2014 showed that dose-dependent decrease in FEV₁ remained stable in patients treated with ponesimod for up to approximately 4 years and were reversible after treatment discontinuation.

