3.7.2 Treating neurologist

The treating neurologist is an experienced neurologist who may be the principal investigator. The treating neurologist is responsible for subject clinical care and management, e.g., eligibility evaluation, supervision of study drug administration, assessing and reporting MS relapses on the specific MS relapses pages of the electronic case report form [eCRF; see Sections 7.2.2 and 10.1.6], monitoring of safety, including recording and treating of AEs (with the exception of non-serious AEs with onset after study drug intake and resolution prior to discharge from cardiac monitoring on Day 1 or on the first day of re-initiation of study drug when post-dose monitoring is required, which will be recorded by the first-dose administrator), physical examination, routine laboratory results (with the exception of WBC and lymphocyte counts), concomitant medications, blood pressure (BP), and ECGs (with the exception of BP and post-dose ECG on Visit 3 [Day 1] or on first day of re-initiation of study drug when post-dose monitoring is required, which will be performed by the first-dose administrator). Depending on the site setting, all BP and ECG assessments required by the protocol during the study may be conducted by the first-dose administrator [see Section 3.7.4]. The treating neurologist will not perform EDSS / FS assessment and will not alter the EDSS or FS scores obtained by the efficacy assessor [see Section 7.2.2]. The treating neurologist will not have access to MRI data throughout the study, unless necessary for safety reasons.

It is the responsibility of the treating neurologist to explain the study in all its aspects to the subject and obtain her/his informed consent. The treating neurologist will be responsible for emphasizing the need for reliable contraception methods and explaining such methods to the female participants who are WOCBP for the period defined in this protocol [Section 4.5].

The treating neurologist is responsible for the medical management of the subject experiencing cardiac events of clinical concern occurring at any time during the study treatment and not already evaluated by the first-dose administrator. In these events, the treating neurologist may consult with the first-dose administrator and/or a cardiologist. In case of acute cardiac events, she/he may refer the subject to a cardiologist to receive emergency care and treatment.

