5.1.4.2 Functional blinding

First-dose effects on HR and AV conduction, and lymphocyte count reduction have been identified as potentially unblinding information. Access to this information by the site's staff and sponsor's study team will be restricted. The following measures will be taken to ensure that the efficacy assessments (i.e., EDSS/FS) are done independently and that cardiac safety assessments, and lymphocyte count assessments are performed and reviewed without potential to introduce a bias:

- The primary endpoint (ARR) and the first secondary endpoint (disability accumulation) are based on the evaluations of the EDSS and FS scores, assessed by an efficacy assessor, not involved in any other aspects of patient care and management throughout the study.
- The subject will be instructed not to discuss AEs (other than those required for EDSS assessments), HR, pulmonary function and/or concomitant medications and any other medical event that have the potential of revealing the treatment allocation with the efficacy assessor.
- The principal investigator / treating neurologist and first-dose administrator evaluating cardiac safety assessments must not discuss any issues related to patient care and management unless mandated for reasons of subject safety. On Day 1 and on the first day of re-initiation of study drug when post-dose monitoring is required, significant findings, which in view of the first-dose administrator meet the definition of an AE, have an onset after the study drug intake and are resolved at the time of discharge of the subject, must be recorded directly on the AE page of the separate eCRF by the first-dose administrator / delegate. These AEs, the ECGs interpretation

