6.1.1 Primary efficacy endpoint

The primary endpoint is ARR. This endpoint is defined as the number of confirmed relapses from randomization up to EOS, per subject-year.

Definition of relapse

- A relapse is defined as new, worsening or recurrent neurological symptoms that occur at least 30 days after the onset of a preceding relapse, and that last at least 24 hours, in the absence of fever or infection.
- The new, worsening or recurrent neurological symptoms are to be evaluated by the treating neurologist and, if all the elements of the above definition have been verified, in the absence of another, better explanation of the subject's symptoms, the event is considered as a relapse [see Section 7.2.2]. The onset date of the relapse corresponds to the onset date of the symptoms.
- A relapse will be confirmed only when the subjects' symptoms are accompanied by an increase in EDSS/FS scores, which is consistent with the subject's symptoms, from a previous clinically stable EDSS/FS assessment (i.e., performed at least 30 days after the onset of any previous relapse), obtained by the efficacy assessor and consistent with the following:
 - an increase of at least half a step (0.5 point; unless EDSS = 0, then an increase of at least 1.0 point is required), or
 - an increase of at least 1.0 point in at least two FS scores, or
 - an increase of at least 2.0 points in at least one FS score (excluding bladder/bowel and cerebral).

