8.4.1 Unscheduled visits for relapses (Visits R1, R2, etc.)

Subjects will be reminded to contact their treating neurologist at the clinical site immediately in the event of appearance of any new or worsened neurological symptoms. Whenever a subject contacts the principal investigator / treating neurologist reporting the appearance of any symptoms suggestive of an MS exacerbation, the principal investigator / treating neurologist will interview the subject and determine the necessity of an unscheduled visit for relapse. An unscheduled visit will be organized as soon as possible after onset or worsening of the symptom(s) as follows:

- The principal investigator / treating neurologist will interview and examine the subject to determine whether or not a relapse may have occurred since last visit using the dedicated relapse assessment questionnaire [see [Appendix 12](#)] and the relapse symptoms form [see [Appendix 13](#)] and decide whether the subject has to be referred to the efficacy assessor.
- In order to exclude potential other reasons for the symptom(s) observed, the principal investigator / treating neurologist will need to perform the following assessments:
 - Physical examination,
 - Vital signs: pulse rate, body temperature.
- In the event of the subject's referral to the efficacy assessor, the latter will perform the EDSS and FS within 7 days after onset or worsening of the symptom(s). The decision regarding whether the new or worsened neurological symptoms are

considered as confirmed or unconfirmed relapse will be made by the principal investigator / treating neurologist by assessing the compatibility of the symptoms reported by the patient and the presence or absence of a qualifying increase in the EDSS/FS (i.e., of the magnitude described in Section 6.1.1) resulting from comparison between the current and previous, clinically stable EDSS/FS assessment performed by the blinded efficacy assessor.

All MS relapses, whether confirmed or unconfirmed during the study, must be reported on specific relapse pages of the eCRF. MS relapses and associated symptoms are not to be entered on the AE page of the eCRF with the following exceptions:

- MS relapses with fatal outcome (these must always be recorded as an AE on the AE page in addition to being reported as SAEs).

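### The confirmation rule for the primary endpoint leaves the reference score open, and the treating neurologist applies it; its numeric part should be fixed and derived by program

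*Protocol*

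**What the plan says.** The Protocol divides the work on a relapse among several steps.

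- **Referral (7.2.2, Step 2).** The principal investigator or "treating neurologist will determine if symptoms are likely to be due to a relapse"; only then is the subject sent for scoring.
- **Scoring (7.2.1 and 7.2.2, Step 3).** Only the efficacy assessor scores EDSS and FS, without looking at earlier scores. The treating neurologist may not alter the result.
- **Confirmation (7.2.2, Step 4).** The treating "neurologist will decide if the relapse is confirmed or not, according to the protocol definition of confirmed relapse". Section 8.4.1 repeats this for unscheduled visits: the decision whether the event is "considered as confirmed or unconfirmed relapse will be made by the principal investigator / treating neurologist". It rests on a qualifying score increase and on "assessing the compatibility of the symptoms reported by the patient".
- **Definition (6.1.1).** Confirmation needs "an increase in EDSS/FS scores, which is consistent with the subject's symptoms", a threshold in EDSS or FS points, and a comparison with an earlier stable assessment taken 30 days or more after any previous relapse began.
- **Blinding (5.1.4.2).** The primary endpoint and the first secondary endpoint "are based on the evaluations of the EDSS and FS scores, assessed by an efficacy assessor, not involved in any other aspects" of care. The treating neurologist's two decisions are not mentioned there.
- **What the neurologist sees (3.7.2).** Duties include "monitoring of safety, including recording and treating of AEs" and routine laboratory results other than WBC and lymphocyte counts. Under 5.1.12.4 the investigator acts on lung-function results.

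**The concern.** The confirmed flag is the unit counted in the primary analysis. It is also the event in the second secondary endpoint, and through the 30-day exclusion in 6.1.2 it affects which EDSS scores may confirm disability accumulation. The person who sets it manages safety. Section 3.7.3 withholds adverse events, concomitant medication and laboratory results from the assessor, and 5.1.4.2 tells subjects not to discuss lung function with the assessor, because such information could reveal the allocation.

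Part of what this person decides needs no judgement: whether the increase reaches the threshold, and from which earlier score it is measured. Leaving that part to discretion lets the same scores lead to different calls, and nothing in the listed analyses applies the 6.1.1 threshold uniformly to both arms.

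**Working it through.** **1. Which parts of 6.1.1 can be computed**

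- *Threshold.* EDSS up by 0.5 (1.0 if the earlier EDSS is 0), or two FS scores up by 1.0, or one FS score up by 2.0 (bladder/bowel and cerebral excluded). The scores are in the eCRF (7.2.1), so this is computable.
- *Reference score.* It must be stable and far enough from any earlier relapse. Onset dates are part of the definition. This is computable only once the text says which eligible score to use.
- *Fit with the symptoms.* A clinical judgement, not computable from scores.

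**2. Whether the reference matters**

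EDSS is scored every 12 weeks (7.2.1), so several eligible scores can exist. Invented example: EDSS 2.0 at Week 12, 2.5 at Week 24, no relapse so far, then 2.5 at a relapse visit, with FS changes below the limits. Measured from Week 12 the change is 2.5 − 2.0 = 0.5, which qualifies. Measured from Week 24 it is 2.5 − 2.5 = 0, which does not. Both references satisfy 6.1.1 as worded.

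**3. Information with an arm difference**

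In the Phase 2 study (1.3.2.4), "Accordingly 13.5% of patients in the ponesimod 20 mg group had" an FEV1 below 80% of baseline at least once, against 3.3% on placebo; dyspnea was reported in 6.1% against 3.3%. The same section ties the higher incidence of liver enzyme elevations to 40 mg and gives no 20 mg versus placebo figure.

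**4. The planning model, reproduced**

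Inputs (11.5.1): rates 0.50 and 0.325, k = 1.3, mean follow-up 1.9 years, 300 per arm, two-sided 0.05.

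- Expected counts: 0.50 × 1.9 = 0.95 and 0.325 × 1.9 = 0.6175.
- Var(log RR) = (1/0.95 + 1/0.6175 + 2 × 1.3)/300 = (1.0526 + 1.6194 + 2.6)/300 = 0.01757, so SE = 0.1326.
- |ln 0.65|/SE = 0.4308/0.1326 = 3.25, and Φ(3.25 − 1.96) = 90.1%.

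The Protocol states about 90%. All nine rows of the table in 11.5.3 also reproduce to within 0.1 percentage point.

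**5. Illustration of what differential confirmation would do**

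The percentages of lost confirmations below are assumptions; no document gives one. Suppose no true effect (0.50 in both arms) and a fraction f fewer confirmations on ponesimod. The chance of a significant result is Φ(|ln(1 − f)|/SE − 1.96) + Φ(−|ln(1 − f)|/SE − 1.96).

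- f = 5%: rates 0.50 and 0.475; SE = √[(1.0526 + 1.1080 + 2.6)/300] = 0.1260; 0.0513/0.1260 = 0.407; result 6.9%.
- By the same formula: f = 2% gives 5.3%, f = 10% gives 13.2%, f = 20% gives 41.1%.

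With a true rate ratio of 0.65, f = 5% shows as 0.65 × 0.95 = 0.6175 (a 38% reduction) and f = 10% as 0.65 × 0.90 = 0.585 (about 42%). A shift of 5% the other way gives 0.65 × 1.05 = 0.6825 (about 32%). The direction is as unknown as the size.

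**6. The planned checks**

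- 11.3.2.2.2 compares between arms the proportions of reported symptoms called relapses and called confirmed relapses. A difference could come from the drug or from the calls; the comparison cannot separate the two.
- 11.3.2.4 repeats the analysis on all relapses, confirmed or not. That avoids Step 4 by dropping confirmation, so it is a different count, and it still depends on Step 2.

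**The case against.** The case for leaving the text alone is substantial. The neurologist is formally blinded and cannot touch the scores, and nothing is confirmed without a qualifying change in them. First-dose cardiac findings, WBC and lymphocyte counts (apart from alerts) and MRI data are restricted. Most subjects on 20 mg never show the lung signal: 100 − 13.5 = 86.5%. Section 11 leaves derivation algorithms to the SAP, which is not at hand and may already hold a programmed check. Programming a threshold removes the step where bias is least plausible.

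These points stand and keep this a minor matter. They do not settle the open reference score, which is protocol wording.

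A reader might infer more than the documents support:

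- *That confirmation could be derived from the scores alone.* Sections 6.1.1, 7.2.2 and 8.4.1 all require the change to fit the symptoms.
- *That 5.1.4.2 is false.* The endpoint does rest on the assessor's scores. The section is incomplete, because it omits the neurologist's decisions.
- *That liver findings reveal the 20 mg arm.* No figure for 20 mg against placebo is given.
- *That differential confirmation is ignored.* Section 11.3.2.2.2 covers confirmed relapses explicitly, though without applying the rule uniformly.
- *That programming the threshold protects the whole process.* The Step 2 referral, a larger discretionary step, stays with the same person.

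**Conclusion.** The point holds as a low-cost improvement, not as an error that invalidates the primary analysis. The Protocol fixes that the treating neurologist judges the qualifying increase and sets the flag, and 6.1.1 does not fix the reference score. Together these leave discretion in the primary count that serves no clinical purpose.

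The size of any bias cannot be estimated from the documents. The 5.3% to 41.1% range shows only how the test would respond to assumed losses of 2% to 20% of confirmations in one arm, with dispersion and follow-up as planned and the placebo arm unaffected. It is not evidence that such losses would occur.

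**What to change.** 1. In 6.1.1, name the reference: the most recent assessor score before the event that lies 30 days or more after the start of any earlier relapse.
2. For analysis, derive the threshold by program from the assessor's eCRF scores. Count a relapse as confirmed when that criterion is met and the neurologist judged the change consistent with the symptoms. Use the same flag wherever confirmed relapses enter a secondary endpoint.
3. List discordances between the derived criterion and the neurologist's call, and query them before unblinding. Section 7.2.2 describes only three recorded outcomes (none, unconfirmed, confirmed), so the query must establish whether an unconfirmed call rested on the threshold or on the symptoms.
4. Run the count on the neurologist's own flag as a sensitivity analysis.
5. State in 5.1.4.2 that the treating neurologist makes the referral and symptom-consistency decisions.

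The neurologist's decision at the visit, which triggers re-consent under 7.2.2, is unchanged. The cost is some programming, short text changes in two sections and a few discordant cases to query.
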